Study design	This is a prospective, open label trial evaluating home telemonitoring for patients with COPD and history of increased exacerbation risk. The purpose of this study is to determine whether automated home monitoring of medication compliance and biometric parameters (FEV1, FVC, PIFR, IC, pulse oximetry, and symptoms) is acceptable to patients, can improve adherence, and may improve clinical outcomes and reduce avoidable 30-day readmissions. Slow spirometry will be performed Sundays, Mondays, Wednesdays, Fridays and Saturdays. Forced spirometry will be performed Tuesdays and Thursdays.
Number of Sites	Single Site: UNC Hospitals Pulmonary Specialty Clinic
Planned sample size	Twelve (12) patients
Total study duration	The study should be completed within nine (9) months.
Subject Participation Duration	Each patient will be enrolled for three (3) months following enrollment in the study.
Study Technology	A home telehealthcare tablet platform (GoHome) that will collect: 
Multiple spirometry tests each week including both forced and slow spirometry measurementsPulse OximetryQoL Questionnaire responses The platform will: 
Remind patients to take their medicationsRemind patients to perform measurementsSend patients helpful information

	
 Execute a UNC clinic established COPD Action Plan 
The backend of the platform is a remote server (MTI CarePortal) that collects the data, send out alerts to the Principal Investigator and can track and trend the data for them. It also sends out the medication and measurement reminders.

Concomitant Medications	
 Patients can remain on all prescribed medications Medications can be changed during the study when clinically indicated by study PI or patient provider
Primary Endpoint	
 Adherence to all measurement collection Quality of Life scores
Secondary Endpoint	
 Patient satisfaction with monitoring system Thirty (30) day exacerbation
Exploratory Endpoints	
 Thirty (30) day exacerbation stratified by FEV1 Adherence to subcomponent measurements Quality of home forced spirometry measures Variability in slow spirometry and correlation of change in slow spirometry values with COPD exacerbation Quality of life scores at each visit Total number of clinical interventions by type (what the medical staff does in response to the telemonitoring) Peak inspiratory flow measurements Adherence to taking prescribed medications
Patient Selection Criteria	
Inclusion Criteria:
 
 Male or Female patients 40 to 80 years of age English speaking Spirometry confirmed COPD (post-BD FEV1/FVC<0.70) and post-BD FEV1% predicted <80% at screening visit. (Target 50% of recruitment with post-BD FEV1<50% predicted (severe obstruction). Spirometry must have been collected within 24 months prior to screening. Increased COPD exacerbation risk defined as either of the following in the prior 12 months: 
 One hospitalization for COPD exacerbation Two outpatient COPD exacerbations requiring treatment with steroids and/or antibiotics Signed informed consent 
Exclusion Criteria:
 
 Unable to perform spirometry on their own following training. Planned discharge to a nursing home or other extended care facility Co-morbid conditions likely to result in non-preventable

	
readmissions (e.g., terminal malignancy, cirrhosis or end-stage liver disease, chronic wound infections, etc.)
 
 • Uncontrolled or untreated medical conditions that would predispose the patient to recurrent COPD exacerbations (i.e., bronchiectasis) • Patient refusal to or inability to comply with monitoring requirements, for any reason including but not limited to dementia, a history of dementia, or other significant mental impairment • Patients enrolled in any other clinical trials or therapeutic studies of drugs, devices, or biologics
Safety Monitoring	As this study is deemed low risk, oversight for this feasibility study will be conducted by the PI ([name]). The PI will monitor data to ensure the safety of participants.
Sample Size Justification	This is a technical evaluation intended to determine if telehealth monitoring can be integrated into the home monitoring of patients with COPD and determine both the acceptance and value of its use. The sample size is not powered or intended to establish statistically significant differences from historic experience.
Statistical Analysis	
The sample size of this technical evaluation is not powered or nor intended to establish statistically significant differences. The adherence and utilization of the platform, as defined by the physiologic and QoL measurements, will be helpful in establishing guidance for future efficacy trials. Nevertheless, descriptive characteristics of the patients prior to, during, and at the end of the study will be tabulated.
 
The study is based on two primary endpoints, adherence to home device measurement collection and baseline to Week 12 change in Total Score of COPD Assessment Test (CAT). Home device measurement adherence is described as percentage of participants achieving >50% completion of all planned device measurements (spirometry, pulse oximetry and questionnaires) over three months. Change in CAT score is defined as percentage of participants achieving ≥ 2 point decrease in CAT from baseline to three months. Additional secondary and exploratory outcomes are also identified in the full protocol.
 
The primary outcome will be reported as proportion with 95% confidence intervals. Other outcomes will be described with proportion and 95% confidence interval, rate, or descriptive summary measures as defined in the full protocol. All tests with p value < 0.05 will be interpreted nominally as statistically significant. In addition, the results will be used to identify technological deficiencies and provide data to inform the power requirements for future studies.

2. Table of Contents

1	Protocol Synopsis	2
2.	Table of Contents	5
3.	List of Abbreviations	7
4.	Introduction	8
4.1.	Background	8
4.2.	Study Design.....	8
5.	Study Endpoints	9
5.1.	The specific Primary Endpoints of this study are:.....	9
5.2.	The specific Secondary Endpoints of this study are:.....	9
6.	Selection of Study Population.....	9
6.1.	Inclusion Criteria:.....	9
6.2.	Exclusion Criteria:.....	9
7.	Study Procedures:	10
7.1.	Patient Identification and Informed Consent	10
7.2.	Study Home Equipment	10
7.3.	Study Data Platform.....	11
7.4.	Study Procedure.....	11
8.	Quality Control Measures	12
9.	Assessments.....	12

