Differences between important continuous variables at two specific times will be evaluated with the two-sided paired t-test ($P<0.05$). Important categorical events such as changes in FEV1, Inspiratory Capacity, QoL, medication adherence, rehospitalization and incidence of adverse events will be evaluated by constructing 95% confidence limits in their incidence, and also with descriptive statistics. In addition, the results will be used to identify technological deficiencies and provide data to inform the power requirements for future studies.

Primary Endpoint Definitions

The first primary endpoint variable for this study is the change from baseline in Total Score of COPD Assessment Test (CAT). The total CAT score is calculated by summing the scores of all items and ranges from 0 to 40, higher scores indicating severe condition. The change will be calculated as the CAT score at Week 12 minus the CAT score at Enrollment. A negative change in CAT score will indicate an improvement in patient status.

The second primary endpoint variable for this study is adherence to performing scheduled measurements and responding to scheduled questionnaires. For each subject the adherence will be recorded based on the data uploaded to the CarePortal. The adherence percentage will be calculated by the difference in recorded measurements and answered questionnaires versus the scheduled measurements and questionnaires.

Analysis of Primary Endpoints

The primary outcomes will be reported as proportions with 95% confidence intervals, on the FAS.

Secondary Endpoint Definitions

The prespecified secondary endpoints for this study will include:

- Participant satisfaction survey scores at 3 months (Time frame: 3 months) defined as the percentage of participants with score of 4 or higher on individual survey domains. A satisfaction survey (investigator-developed, 15 questions, each question is graded on a scale of 1-5, 1 being not at all and 5 being extremely) will be used to measure home spirometry and table ease and usefulness.
- Rate of self-reported COPD exacerbations (Time frame: 3 months) defined as the 30-day COPD exacerbation rate, defined as the mean number of events/30 days of follow-up (using three months of follow-up data). COPD exacerbation events are defined as self-reported COPD exacerbations requiring treatment with antibiotics or steroids.

Analysis of Secondary Endpoints

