- Descriptive analysis of change from baseline to weeks 4, 8 and 12 on CAT Total score including mean (SD), median (IQR), range
- Descriptive analysis of Inspiratory Capacity measurements, including mean (SD), median (IQR), range, coefficient of variation
- The overall median of Inspiratory Capacity in the week before, of, and after each exacerbation will be calculated and compared using Kruskall-Wallis testing.
- The total number and distribution of type of intervention (phone contact, clinic visit, referral to Emergency Department) will be summarized in tabular format
- The proportion of suboptimal peak inspiratory flow measurements (defined as <3.27L/sec) will be reported with 95% CI. Additional exploratory analyses include distribution of peak inspiratory flow measurements along with proportions of alternative thresholds.
- Descriptive analysis of overall maintenance inhaler adherence including mean (SD), median (IQR), range, proportion and 95% CI of participants with >50% adherence
- Descriptive analysis of change from baseline to week 12 on number of days per week of maintenance inhaler adherence including mean (SD), median (IQR), range
- Tabular summary of overall rescue inhaler use (categorized into not at all, once a week or less, 2-3 times per week, 1-2 times per day, 3 or more times per day)
- Comparative analysis (chi square) of distribution of categorical responses to rescue inhaler use comparing baseline to 12 week visit
- Tabular summary of number and type of SAE

14. Safety Monitoring

As this study is deemed low risk, using technology frequently prescribed for use by COPD patients at home, oversight for this feasibility study will be conducted by the PI ([name]). The PI will monitor data to ensure the safety of participants. Only treatment-related serious adverse events (SAEs) will be reported to the IRB using the Adverse Event Template Form, per institutional and national guidelines within one business day of notification of the event. Hospitalization for COPD exacerbation will be considered an SAE. SAEs will be tracked for 30 days following termination of the study.

15. Administrative Requirements

15.1. *Ethical Considerations*

The study will be conducted in accordance with the ethical principles founded in the Declaration of Helsinki, and according to local applicable laws and regulations. The institutional

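### The lead CAT result is an uncontrolled, one-directional responder proportion, while the numerical change that Section 13 defines as primary is summarised only as exploratory and without a confidence interval

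*Combined protocol and SAP*

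**What the plan says.** The Statistical Analysis row of the synopsis names the baseline to Week 12 change in CAT as one of two primary endpoints. It then turns that change into a responder measure: the "percentage of participants achieving ≥ 2 point decrease in CAT from baseline to three months".

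Section 13, under Primary Endpoint Definitions, gives a numerical variable: "The change will be calculated as the CAT score at Week 12 minus the CAT score at Enrollment". A negative value means improvement. No 2-point cut-off appears there. Under Analysis of Primary Endpoints the section says: "The primary outcomes will be reported as proportions with 95% confidence intervals, on the FAS".

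The numerical change returns under Analysis of Exploratory Endpoints: "Descriptive analysis of change from baseline to weeks 4, 8 and 12 on CAT Total score including mean (SD), median (IQR), range". No confidence interval is attached to it. The matching exploratory definition speaks of a median with an SD, which does not quite agree with that line.

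Section 13 also has a general provision: "Differences between important continuous variables at two specific times will be evaluated with the two-sided paired t-test". It does not name CAT. The next sentence lists changes in QoL among categorical events, to be described by their incidence with 95% confidence limits and also by descriptive statistics.

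On design, the synopsis says: "This is a prospective, open label trial evaluating home telemonitoring for patients with COPD". No comparator arm or reference responder rate is described. The planned sample is 12, stated not to be powered for significant differences.

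**The concern.** Two things look wrong.

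First, Section 13 cannot be carried out on its own. It defines a number, asks for a proportion, and leaves the rule that links them to the synopsis.

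Second, the lead summary counts movement in one direction only. CAT scores will move between two visits 12 weeks apart even if the group does not change on average, and every fall of 2 points or more counts as a response. With no control arm, no benchmark and no matching count of patients who rise by 2 points or more, the reader cannot tell a benefit from symmetric movement. A result of 4 of 12 could be read as a third of patients having improved.

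This matters because improving quality of life is a stated secondary objective, CAT is a primary endpoint, and the study means to judge the value of the system as well as its acceptance.

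**Working it through.** The documents give no responder rate, SD or effect size for CAT, so there is no figure of the plan's own to reproduce. The check asks how large the responder proportion would be if the mean change were zero.

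**Inputs from the documents**
- n = 12 (synopsis, planned sample size).
- Response = decrease of 2 points or more (synopsis).
- Scale: "The total CAT score is calculated by summing the scores of all items and ranges from 0 to 40" (Section 13). With 8 items scored 0 to 5 (Section 9.2.5), totals are whole numbers.

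**Assumptions**
- True mean change 0, and change approximately normal.
- SD of change 3 to 7 points, with 2 and 10 as outer values. The documents give no SD.
- All 12 patients have both scores.

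**Step 1: responder proportion at zero mean change.** For whole-number scores, a change of -2 or lower corresponds to a cut at -1.5 on the continuous scale, so P = Φ(-1.5/SD).

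| SD | -1.5/SD | P | 12 × P |
|---|---|---|---|
| 2 | -0.750 | 22.7% | 2.7 |
| 3 | -0.500 | 30.9% | 3.7 |
| 5 | -0.300 | 38.2% | 4.6 |
| 7 | -0.214 | 41.5% | 5.0 |
| 10 | -0.150 | 44.0% | 5.3 |

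Without the whole-number correction, Φ(-2/SD) gives 16% at SD 2, 25% at SD 3, 34% at SD 5, 39% at SD 7 and 42% at SD 10. The message is the same.

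By symmetry, the expected proportion with an increase of 2 points or more equals P. Showing both proportions would therefore reveal movement without direction; the planned count of decreases alone hides it.

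**Step 2: what the planned interval can show.** Exact (Clopper-Pearson) 95% limits at n = 12:
- 4/12: 9.9% to 65.1%
- 7/12: 27.7% to 84.8%
- 8/12: 34.9% to 90.1%
- 9/12: 42.8% to 94.5%

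At 4/12 the interval covers the whole 31% to 42% band. At least 8 responders are needed for the lower limit to pass 30.9% (SD 3), and 9 for it to pass 41.5% (SD 7). The reader would have to know the SD to make even this comparison.

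**Step 3: the alternative lead estimate.** The half-width of the paired 95% CI for the mean change is t(0.975, 11) × SD/√12 = 2.201 × SD/3.464 = 0.635 × SD.
- SD 3: 1.9 points
- SD 5: 3.2 points
- SD 7: 4.4 points

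This is wide, but it has a natural reference value (zero), shows direction and size, and uses the SD observed in the study instead of an assumed one.

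**The case against.** **The numerical change is already planned.** A reader might infer that CAT change is reported only as a proportion, or that the study will yield no SD for sizing a later trial. The documents do not support either reading. The exploratory analysis prespecifies mean (SD), median (IQR) and range at weeks 4, 8 and 12, and the general paired t-test could well be read as covering CAT. With mean, SD and n reported, anyone can compute the interval. This stands. What remains is narrower: the plan leads with the proportion, and it attaches no interval to the mean change.

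**The definitions can be read together.** Section 13 names the patient-level variable and the synopsis supplies the cut-off; the adherence endpoint is split in the same way. A responder summary of a numerical variable is an ordinary structure. This also largely stands: the gap is an omission that one sentence would close.

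**The 31% to 42% is not a figure from the plan.** True; it depends on an assumed SD. It is also tempting to say that this share of unchanged patients would respond by chance. That does not follow. A zero mean change does not mean that each patient is unchanged, because the SD of change can include real improvements and real worsenings that offset each other. The figure says only what proportion is compatible with no average change.

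**It is a feasibility study.** The plan disclaims power, sets no success threshold for the CAT proportion, and has use of the system as its primary objective. This limits the severity. It does not give the reader of the headline proportion anything to compare it with.

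**A mean change is uncontrolled too.** Correct. Regression to the mean and open-label reporting affect it as well, and at n = 12 it is imprecise.

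**Conclusion.** The point holds as a minor one. The primary CAT analysis is a one-directional responder proportion with no control or benchmark, and its cut-off is stated only in the synopsis. The numerical change that Section 13 names as the primary variable is demoted to an exploratory summary without a confidence interval.

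With zero mean change, normal change, whole-number scores and an SD of 3 to 7 points, about 31% to 42% of patients (3.7 to 5.0 of 12) would count as responders. The range widens to about 23% to 44% for SD 2 to 10. The SD is an assumption throughout; the structural point (no benchmark, one direction) does not depend on it.

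The documents do not support going further, for example by saying that the plan claims benefit from this proportion or that the continuous data are lost.

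**What to change.** In Section 13 and in the synopsis:

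1. Use one CAT definition: change in total score, Week 12 minus Enrollment.
2. Make the mean change with its paired 95% CI the lead CAT estimate. Align the exploratory definition and analysis lines, so that mean goes with SD and median with IQR.
3. Keep the proportion with a decrease of 2 points or more as supportive, stating the cut-off in Section 13, and show beside it the proportion with an increase of 2 points or more, each with its 95% CI.
4. State that, without a control group, neither summary alone is evidence of benefit.

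Cost: a few sentences and one or two extra table lines. No new data are needed. The lead estimate remains uncontrolled and imprecise at n = 12, and the text should say so.

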4.2. Study Design

This is a prospective, open label trial evaluating home telemonitoring for patients with COPD and a history of increased exacerbation risk. The purpose of this study is to determine whether automated home monitoring of medication compliance and biometric parameters (FEV1, FVC, PIFR, IC, pulse oximetry, and symptoms) is acceptable to patients, can improve adherence, and may improve clinical outcomes and reduce exacerbations and avoidable 30-day readmissions. Slow spirometry will be performed Sundays, Mondays, Wednesdays, Fridays and Saturdays. Forced spirometry will be performed Tuesdays and Thursdays.

5. Study Endpoints

5.1. The specific Primary Endpoints of this study are:

- Adherence to measurement collection
- Quality of Life scores

5.2. The specific Secondary Endpoints of this study are:

- Variability in slow spirometry and correlation of change in slow spirometry values with COPD exacerbation
- Patient satisfaction with the monitoring system
- Thirty (30) day exacerbations
- Total number of clinical interventions by type (what the medical staff does in response to the telemonitoring)
- Ability for early identification of loss of DPI effectiveness
- Adherence to taking prescribed medications

6. Selection of Study Population

Eligible participants include those being managed for COPD by the UNC Hospitals Pulmonary Specialty Clinic in Chapel Hill, NC and who have been identified to be at a higher risk of exacerbation of their COPD. We plan to enroll twelve (12) patients for three (3) months of monitoring each. The study will be at a single center and anticipated to be completed within nine (9) months.

6.1. Inclusion Criteria:

- Male or Female patients
- 40 to 80 years of age
- English
- Spirometry confirmed COPD (post-BD FEV1/FVC<0.70) and post-BD FEV1% predicted <80% at screening visit. (Target 50% of recruitment with post-BD FEV1<50% predicted (severe obstruction). Spirometry must have been collected within 24 months prior to screening.
- Increased COPD exacerbation risk defined as either of the following in the prior 12 months:
 - One hospitalization for COPD exacerbation
 - Two outpatient COPD exacerbations requiring treatment with steroids and/or antibiotics
- Signed informed consent

6.2. Exclusion Criteria:

- Unable to perform spirometry on their own following training.
- Co-morbid conditions likely to result in non-preventable readmissions (e.g., terminal malignancy, cirrhosis or end-stage liver disease, chronic wound infections, etc.)

- Uncontrolled or untreated medical conditions that would predispose the patient to recurrent COPD exacerbations (e.g., bronchiectasis)
- Patient refusal to or inability to comply with monitoring requirements, for any reason including but not limited to dementia, a history of dementia, or other significant mental impairment
- Patients enrolled in any other clinical trials or therapeutic studies of drugs, devices, or biologics

7. Study Procedures:

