teaching tips as part of the COPD Action Plan will also be incorporated into the GoHome software to educate and motivate patients regarding self-care. A Quality of Life questionnaire (COPD Assessment Test) will also be collected every 4 weeks from the patients through the GoHome tablet.

At the end of study (after completion of final phone visit), the patients will return the equipment to UNC via a pre-paid FedEx air bill that has been included with the original shipment. A member of the Clinic research study team will have a final call with the patient to check on the patient's respiratory status and have them complete a usability questionnaire by phone.

8. Quality Control Measures

Quality control of the lung function measurements will include automatic ATS/ERS intra-measurement grading of the forced flow-volume loops and slow spirometry to ensure interpretable and actionable home spirometry.⁵ MTI will assist with determining the number of missed spirometry sessions with seven times per week testing, and determining any technical issues in transmission of data from the spirometer to the MTI CarePortal.

The GoSpiro home spirometer meets the 2019 ATS/ERS criteria for accuracy and reproducibility.⁵ Baseline pulmonary function will be defined as the mean FEV1 over the first two weeks of the study (six measurements). If older data is available for the patient, that data may be included in establishing historic values for analysis. Variability of pulmonary function for alerts to Clinic staff will include a decrease by one personalized z-score using pulmonary function measurements for an individual patient and calculated over the length of the study as well as using historic data if available.

Alerts from acute declines in pulmonary function will be defined as any decrement in either FEV1, FVC or IC >10%. Oxygen saturation readings below 88% will trigger an alert. For patients being managed with DPI delivered inhaled drugs, monitoring of peak inspiratory flow for detection of inadequate flows to aerosolize and deliver the powder, will also generate alerts. The MTI CarePortal will provide daily reports to the Clinic research staff of patient trending towards alert levels, as well as patients with low adherence to medications or measurements.

9. Assessments

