9.2. Clinical Assessments and Interventions

9.2.1. Patient Characteristics and Medical History

Demographic information (age, gender, race) will be captured at Screening. Relevant medical history, prescription drugs, including history of smoking, other pertinent history and information regarding underlying diseases will be recorded at Screening.

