10.3. Record Retention

The PI will maintain all study records according to GCP guidelines.

11. Withdrawal from Study

Patients should immediately be withdrawn from the study for any of the following reasons.

- A condition or adverse event that would prevent the patient from performing the

- specified measurements in the protocol
- At the discretion of the patient
- At the discretion of the Investigator, if deemed appropriate, for any reason

If a patient is withdrawn because of an adverse event, the patient will be followed and treated by the Investigator until the abnormal parameter or symptom has resolved or stabilized. The adverse events must be followed to resolution and the follow-up evaluations should be performed when the patient has stabilized.

Any patient that is withdrawn from the study within the first two weeks due to technical or training reasons will be replaced.

If for any reason a patient does not complete the study, the reason will be entered on the CRF. All patients are free to withdraw from participation at any time, for any reason, specified or unspecified, and without prejudice. The Investigator must record the reason for the early termination.

12. Concomitant Medications

Patients can remain on all prescribed medications. Medications can be changed during the study when clinically indicated by the study PI or patient provider.

13. Statistical Considerations:

This is a technical evaluation intended to determine if remote patient monitoring can be integrated into the home monitoring of patients with COPD and determine both the acceptance and value of its use. The sample size is not powered or intended to establish statistically significant differences from historic experience. The adherence and utilization of the platform, as defined by the physiologic and QoL measurements, will be helpful in establishing guidance for future efficacy trials.

Nevertheless, descriptive characteristics of the patients prior to, during, and at the end of the study will be tabulated. Using the full analytical set (FAS), specific variables (demographics and clinical variables, baseline maintenance and rescue inhaler use, and modified Medical Research Council Score) will be summarized using descriptive measures (mean and standard deviation, min, max, median) and graphical displays (boxplots, histograms) as appropriate.

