- Inspiratory Capacity before, during and after COPD exacerbations defined as the overall median Inspiratory Capacity reported at three time intervals: the week before COPD exacerbation, the week of COPD exacerbation, and the week after COPD exacerbation.
- Number of clinical interventions defined as the total number of clinical interventions per participant over study duration. Clinical interventions will be categorized into one of three types (phone contact, clinic visit, referral to Emergency Department).
- Type of clinical interventions defined as the percentage of type of clinical intervention across all study participants. Clinical interventions will be categorized into one of three types (phone contact, clinic visit, referral to Emergency Department).
- Suboptimal peak inspiratory flow measurements defined as the percentage of peak inspiratory flow measurements <3.27 liter/sec obtained on forced spirometry maneuvers.
- Maintenance inhaler adherence defined as the adherence will be defined by average number of days per week (range 0-7) participant reports maintenance inhaler use.
- Change from baseline in maintenance inhaler adherence defined as the change from baseline to 3 months in maintenance inhaler adherence. Adherence will be defined by number of days per week (range 0-7) participant reports maintenance inhaler use.
- Change from baseline in rescue inhaler use defined as the change from baseline to 3 months in rescue inhaler use. Rescue inhaler use will be categorized at baseline and 3 month visit as not at all, once a week or less, 2-3 times per week, 1-2 times per day, 3 or more times per day.

Analysis of Exploratory Endpoints

The exploratory endpoints will be analyzed as described below. The hypothesis testing of these additional secondary efficacy endpoints is considered exploratory. All tests with p value < 0.05 will be interpreted nominally as statistically significant.

- For stratified COPD exacerbation analyses, the proportion of patients with COPD exacerbations and the rate of exacerbations occurring during follow-up will be reported along with 95% CI stratified by FEV1 severity (<50% predicted: >=50% predicted).
- Individual home assessment component adherence will be reported as proportions with 95% confidence intervals
- Quality of home forced spirometry measures will be reported as proportions with 95% confidence intervals

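### Section 5.2 lists early identification of loss of DPI effectiveness as a secondary endpoint, but nothing defines or analyses it, and the exploratory peak-flow summaries are not split by DPI use, by participant or by time

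*Combined protocol and SAP*

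**What the plan says.** Section 5.2 names six secondary endpoints, one of which is "Ability for early identification of loss of DPI effectiveness". The synopsis gives two secondary endpoints, satisfaction and 30-day exacerbation. Section 13 introduces its own list with "The prespecified secondary endpoints for this study will include" and gives the same two.

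Peak inspiratory flow appears in Section 13 only among the exploratory endpoints, defined as "Suboptimal peak inspiratory flow measurements defined as the percentage of peak inspiratory flow measurements <3.27 liter/sec obtained on forced spirometry maneuvers". The planned analysis is: "The proportion of suboptimal peak inspiratory flow measurements (defined as <3.27L/sec) will be reported with 95% CI". It continues: "Additional exploratory analyses include distribution of peak inspiratory flow measurements along with proportions of alternative thresholds".

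Section 8 gives peak flow a DPI-specific operational role: "For patients being managed with DPI delivered inhaled drugs, monitoring of peak inspiratory flow for detection of inadequate flows" is to generate alerts. It states no flow threshold for those alerts, and Section 13 plans no summary of them.

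No entry criterion in Section 6.1 or 6.2 concerns inhaler type, and Section 12 says "Patients can remain on all prescribed medications". Section 9.2.1 records "Relevant medical history, prescription drugs, including history of smoking" at Screening, and Section 7.4 has the nurse ask about changes in inhaled medication every four weeks.

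**The concern.** An endpoint about early identification of loss needs four things: a definition of the loss, the group in whom it can occur, a starting value for each person, and a time at which the change is detected. Section 5.2 supplies none of these, and no later section fills the gap.

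A reader looking for the result would turn to the exploratory peak-flow percentage. That figure answers another question: how often readings, from whoever supplied them, fall below a fixed value. It cannot show whether DPI users had low flows, whether anyone declined, or when. It also carries a 95% CI with no stated method for repeated readings from the same person. At stake are a listed endpoint with no reportable result and an exploratory interval that may look much tighter than 12 people can support.

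**Working it through.** The plan states no figure for this endpoint, so there is nothing to reproduce.

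**1. Matching Section 5.2 to Section 13**

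- Slow-spirometry variability and its relation to exacerbation: inspiratory capacity variability, and inspiratory capacity around exacerbations (exploratory).
- Satisfaction: defined (secondary).
- 30-day exacerbations: defined (secondary).
- Clinical interventions by type: defined (exploratory).
- Medication adherence: maintenance inhaler adherence (exploratory).
- Loss of DPI effectiveness: no counterpart.

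The DPI item is the only one of the six with no matching definition.

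**2. Number of readings**

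Inputs: 12 participants (Section 6), 12 weeks of active monitoring (Section 7.4), forced spirometry two days a week (Section 9.2.3). Assumed: full adherence and one peak-flow reading per session.

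- Per participant: 2 × 12 = 24.
- In total: 12 × 24 = 288.

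**3. What a pooled percentage can distinguish**

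The number of DPI users, d, is not given. With low-reading rates pD in users and pN in others, the pooled percentage is (d × pD + (12 − d) × pN) / 12. All rates and splits below are assumptions.

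- d = 6, pD = 40%, pN = 10%: (240 + 60)/12 = 25%.
- d = 6, pD = 10%, pN = 40%: (60 + 240)/12 = 25%.
- d = 6, both 25%: 25%.
- pD = 40%, pN = 10%, with d = 3, 6, 9, 12: 17.5%, 25%, 32.5%, 40%.
- d = 6, pD = 20%, pN = 50%: (120 + 300)/12 = 35%, against 20% in users. This is one illustration, and the direction could be reversed.

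One pooled value therefore fits opposite patterns. If all 12 use a DPI, the problem in this step disappears.

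**4. Timing**

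Six low readings out of 24 give 6/24 = 25% whether they are scattered or are the last six in a row. Only the second pattern suggests a loss.

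**5. Precision**

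Half-width = 1.96 × √(p(1 − p) × D / n), with D = 1 + (24 − 1) × ICC. Assumed: p = 25%. ICC is the within-participant correlation, which is not given. With so few participants the normal approximation is rough, so these values are indicative.

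- 12 participants, n = 288: ±5.0 points at ICC 0; ±14.1 at 0.3; ±17.7 at 0.5 (D = 12.5); ±22.0 at 0.8.
- 9 DPI users, n = 216: ±5.8 at ICC 0; ±20.4 at 0.5.
- 6 DPI users, n = 144: ±7.1 at ICC 0; ±19.9 at 0.3; ±25.0 at 0.5; ±31.2 at 0.8.
- 3 DPI users, n = 72: ±10.0 at ICC 0; ±35.4 at 0.5.

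Counting participants instead, 2 of 6 DPI users flagged gives an exact (Clopper-Pearson) 95% interval of 4% to 78%.

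**The case against.** The strongest reply is that the peak-flow percentage was never offered as the answer to the Section 5.2 item. It is a separate exploratory endpoint, also named in the synopsis. That stands. A reader might infer that the DPI endpoint fails because readings are pooled, but the documents do not link the two. The endpoint fails because it is undefined, and restricting the percentage to DPI users would not by itself define it.

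Other parts of the reply also stand:

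- The synopsis and Section 13 agree on two secondary endpoints, and Section 5.2 is the outlier. Version 2.0 revised the statistical plan, so the item may be left over. It is still current text.
- Section 8 does provide DPI-specific monitoring, and peak flow is collected twice weekly, so a time course will exist. A planned summary of it is what is missing.
- It is tempting to say that DPI users are only part of the sample and that the pooled figure is off by a known amount. The documents give no share, and inclusion of non-users is inferred from unrestricted wording.
- It is also tempting to say that one low-flow participant dominates the percentage. With full adherence, an always-low participant contributes 24/288 = 1/12 = 8.3 points, exactly what a mean of participant percentages would give. With six DPI users the weight rises to 24/144 = 16.7 points. Neither figure shows undue influence.

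The general paired t-test in Section 13 does not close the gap. It names neither peak flow nor DPI use, and a mean difference between two times does not show early identification in a patient.

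**Conclusion.** The point holds in a limited form. The Section 5.2 item is undefined, is absent from the other two secondary lists, and has no analysis. The exploratory peak-flow summaries, as written, are per reading, not split by DPI use, and blind to timing. The Section 8 alerts go unanalysed.

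That the question cannot be answered is true only of the plan as written. Prescribed drugs, changes in inhaled medication and repeated peak flow are all collected. The documents therefore do not support the view that the trial lacks relevant data.

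The size depends on assumptions. The pooled percentage can conceal opposite patterns in users and non-users if both are present. At 25% low readings, an interval that treats 288 readings as independent would be about 3 to 4 times too narrow for an ICC of 0.3 to 0.8 (14.1/5.0 to 22.0/5.0). The consequence is modest, because this is a 12-patient technical evaluation with no power claim and the endpoint is not primary.

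**What to change.** Choose one of two routes.

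1. **Delete** the item from Section 5.2 and align the secondary and exploratory lists in Sections 1, 5.2 and 13.

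2. **Restate** it as an exploratory endpoint about peak inspiratory flow, not drug effectiveness, and align the lists to match. Among participants recorded as using a DPI, report:
   - each participant's percentage of readings below the protocol's own cut-off;
   - the change from that participant's own early-study baseline, with the baseline window stated;
   - the time to the first reading below the cut-off, among those not below it at baseline.

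The baseline is essential: without it, a participant who is low from week 1 would count as a loss. If the two-week window that Section 8 uses for FEV1 is borrowed, it holds 2 × 2 = 4 scheduled forced sessions, whereas Section 8 mentions six measurements, so the count must be settled. Report non-users separately, and say how a change to or from a DPI during follow-up is handled. Base any CI on participants, or use a method that allows for up to 24 correlated readings each.

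The cost is protocol and SAP wording, with no new measurement. There are two drawbacks. The DPI subgroup will be small and its estimates imprecise. Device type must also be derivable from the medication record, since the sections on prescription drugs and medication changes do not name it.
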